Main in- and exclusion criteria	
Inclusion criteria:
 
 • Best Corrected Visual Acuity (BCVA) of 20/63 or better (Snellen equivalent) using ETDRS charts at starting distance of 4 m • Well demarcated area(s) of GA secondary to AMD with no evidence of prior or active choroidal neovascularization (CNV) • At least one patch of GA more than 0.5 disc area (DA) • Sufficiently clear ocular media, adequate pupillary dilation, and fixation to permit quality fundus imaging 
Exclusion Criteria:
 
 • GA in either eye due to causes other than AMD (for example, monogenetic macular dystrophies [e.g., Stargardt disease, cone rod dystrophy] or toxic maculopathies [e.g., chloroquine/hydroxychloroquine maculopathy]) • Receiving active treatment in any studies of investigational drugs for GA/dry AMD
Test product(s):	NA
dose:	NA
mode of administration:	NA
Comparator products:	NA
dose:	NA
mode of administration:	NA
Duration of observation:	12 months
Endpoints	
All of the following endpoints will be assessed for the study eye.
 
Primary:
 
 • Change from baseline in retinal sensitivity in the junctional zone and in the perilesional zone of the largest atrophic loci as assessed by microperimetry at week 12 • Change from baseline in RPE layers thickness in the junctional zone and in the perilesional zone as measured by SS-OCT at week 12 • Change from baseline in photoreceptor layer thickness in the junctional zone and in the perilesional zone as measured by SS-OCT at week 12 
Secondary:
 
 • Change from baseline in retinal sensitivity in the junctional zone and in the perilesional zone of the largest atrophic loci as assessed by microperimetry at week 24 and 48 • Change from baseline in RPE layer thickness in the junctional zone and in the perilesional zone as measured by SS-OCT at week 24 and 48

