1.2 RATIONALE FOR PERFORMING THE STUDY

GA secondary to AMD is an indication with high unmet medical need. Decision making in early clinical trials may be based on quantification of changes in retinal sensitivity or anatomical changes such as thinning of the photoreceptor layer. Retinal sensitivity in a specific area of the retina can be measured by fundus-controlled perimetry (microperimetry). Anatomical changes of retinal or choroidal structures or the RPE can be analysed via OCT imaging, and correlated to changes in light sensitivity.

In order to be able to address future scientific questions, patients will be asked to voluntarily donate biospecimens for banking. If the patient agrees, banked samples may be used for future drug development projects, e.g. to identify patients that are more likely to benefit from a treatment or experience an adverse event (AE), and thereby better match patients with therapies.

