2.1.2 Primary endpoints

All of the following endpoints will be assessed for the study eye.

- Change from baseline in retinal sensitivity in the junctional zone and in the perilesional zone of the largest atrophic loci as assessed by microperimetry for the evaluation of macular functional response at week 12
- Change from baseline in RPE layer thickness in the junctional zone and in the perilesional zone as measured by SS-OCT at week 12
- Change from baseline in photoreceptor layer thickness in the junctional zone and in the perilesional zone as measured by SS-OCT at week 12

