2.1.3 Secondary endpoints

[figure not shown]
All of the following endpoints will be assessed for the study eye.

- Change from baseline in retinal sensitivity in the junctional zone and in the perilesional zone of the largest atrophic loci as assessed by microperimetry at week 24 and 48
- Change from baseline in RPE layer thickness in the junctional zone and in the perilesional zone as measured by SS-OCT at week 24 and 48
- Change from baseline in photoreceptor layer thickness in the junctional zone and in the perilesional zone as measured by SS-OCT at week 24 and 48
- Change from baseline in the GA area as measured by Fundus Autofluorescence (FAF) at week 12, 24 and 48
- Change in Best Corrected Visual Acuity (BCVA) score as assessed by Early Treatment Diabetic Retinopathy Scale (ETDRS) chart at a starting distance of 4 m at week 12, 24 and 48
- Change in Low Luminance Visual Acuity (LLVA) score as assessed by ETDRS chart under low luminance conditions at a starting distance of 4 m at week 12, 24 and 48
- Number of scotomatous points assessed by microperimetry at week 12, 24 and 48
- Change from baseline in the area of choroidal non-perfusion as measured via Optical Coherence Tomography Angiography (OCT-A) at week 12, 24 and 48

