3.2.2 Inclusion criteria

1. Signed and dated written informed consent in accordance with ICH-GCP and local legislation prior to admission to the study
2. Age ≥ 60 years
3. Ability (including a sufficient general health status according to investigators judgement) and willingness to undertake all scheduled visits and assessments including predefined methodology and standards utilizing microperimetry

4. GA secondary to AMD with no evidence of prior or active choroidal neovascularization (CNV) in the study eye
5. GA lesion in the study eye must reside completely within the FAF imaging field (Field 2-30 degree image centered on the fovea)
6. BCVA of 20/63 or better (Snellen equivalent) using ETDRS charts at starting distance of 4 m in the study eye
7. Well demarcated area(s) of GA secondary to AMD with no evidence of prior or active CNV in the study eye
 - The total GA lesion size $\geq 1.2 \text{ mm}^2$ (approximately ≥ 0.5 disc area [DA]) and $\leq 17.78 \text{ mm}^2$ (approximately ≤ 7 DA) and must reside completely within the FAF imaging field (Field 2–30 degree image centered on the fovea)
 - If GA is multifocal, at least 1 focal lesion must be $\geq 1.2 \text{ mm}^2$ (approximately ≥ 0.5 DA)
8. Sufficiently clear ocular media, adequate pupillary dilation, and fixation to permit quality fundus imaging in the study eye

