7.3.1 Primary endpoint analyses

For each primary endpoint (see [section 2.1.2](#)), baseline is defined as the measurement obtained at Visit 2.

The following descriptive statistics will be calculated for the measurements related to the primary endpoints at each time point, as well as for the changes from baseline: N, arithmetic mean, Standard Deviation (SD), minimum, median, maximum, percentiles, arithmetic coefficient of variation.

Correlations (both Pearson and rank-based) of the changes from baseline of retinal sensitivity in the junctional zone and in the perilesional zone, respectively, of the largest atrophic loci as measured by microperimetry to the following endpoints will be estimated:

- Change from baseline in RPE layer thickness in the junctional zone and in the perilesional zone, respectively, as measured by SS-OCT and by SD-OCT
- Change from baseline in photoreceptor layer thickness in the junctional zone and in the perilesional zone, respectively, as measured by SS-OCT and by SD-OCT
- Changes from baseline in GA area as measured by FAF
- Change from baseline in the area of choriocapillaris flow deficits as measured via OCT-A at week 12, 24 and 48

Individual data as well as summary statistics will be visualised in respective graphical presentations, e.g. scatter plots or box-plots.

Correlations between the primary endpoints and continuous baseline characteristics will be investigated if necessary.

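### Do the structure-function correlations in 7.3.1 pair sensitivity and layer thickness from different lesions in multifocal eyes?

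*Combined protocol and SAP*

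**What the plan says.** Section 2.1.2 defines the sensitivity endpoint as change "in the junctional zone and in the perilesional zone of the largest atrophic loci as assessed by microperimetry". The RPE endpoint next to it reads "Change from baseline in RPE layer thickness in the junctional zone and in the perilesional zone as measured by SS-OCT at week 12", with no lesion named, and the photoreceptor endpoint follows the same pattern. The synopsis ("Change from baseline in RPE layers thickness in the junctional zone and in the perilesional zone as measured by SS-OCT at week 12") and section 2.1.3 ("Change from baseline in photoreceptor layer thickness in the junctional zone and in the perilesional zone as measured by SS-OCT") repeat the asymmetry.

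Section 7.3.1 carries it into the correlations. The sensitivity side is limited by zone, "respectively, of the largest atrophic loci as measured by microperimetry to the following endpoints will be estimated". The thickness side is given as "Change from baseline in RPE layer thickness in the junctional zone and in the perilesional zone, respectively, as measured by SS-OCT", with SD-OCT added and a parallel item for the photoreceptor layer. Zone is paired with zone; nothing explicitly pairs lesion with lesion.

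Inclusion criterion 7 in section 3.2.2 admits multifocal eyes: "If GA is multifocal, at least 1 focal lesion must be" at least 1.2 mm². Section 1.2 gives the correlations their purpose, saying that anatomical changes "can be analysed via OCT imaging, and correlated to changes in light sensitivity". Section 7.2 states that all analyses are exploratory.

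**The concern.** A structure-function correlation is easiest to interpret when both measurements come from the same retina. If thickness were averaged around every lesion while sensitivity came only from the largest, the extra lesions would usually dilute the correlation, and the estimate would depend partly on the mix of unifocal and multifocal eyes. More patients would not remove such an effect. Two analysts working from the protocol text alone could also choose different regions. Section 7.4 plans preliminary looks at the 12- and 24-week data for internal decisions, so a choice made after seeing data would be unwelcome.

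At stake is the size of an exploratory correlation that may inform how these biomarkers are used in early trials. Unifocal eyes are not affected.

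**Working it through.** **The plan's own figure.** The only computed figure is in Table 7.5: 1: 47 patients for a 95% CI half-width d = 0.3 dB at SD 0.9 dB, with 90% probability. The rule is the smallest n with P(χ² on n−1 df ≤ n(n−1)d² / (t²·SD²)) ≥ 0.90, where t is the 97.5% point on n−1 df. At n = 47, t = 2.013 and the bound is 47 × 46 × 0.09 / (2.013² × 0.81) = 59.3, giving probability 0.910. At n = 46 it is 0.887. So 47 is reproduced, and the same rule matches all 12 cells. At the planned 50 the probability is 0.958. This calculation concerns mean sensitivity change only, so the lesion question does not touch the sample size.

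**The text side by side.** The lead sentence of 7.3.1 introduces the junctional and perilesional zones of the largest lesion(s). The bullets beneath it refer again to those two zones in the same order. One reading is that they are the same zones; another is that the missing qualifier is deliberate. No sentence says that thickness is pooled over lesions.

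**Size if the regions did differ.** The document gives no multifocal share, lesion count or thickness noise, so every input here is assumed:
- m: share of multifocal eyes, 0.5 unless stated.
- w: weight of the largest lesion in the pooled thickness, 0.5, 0.6 or 0.7.
- c: correlation of true thickness change between lesions of one eye, 0.3, 0.4 or 0.5.
- k: noise variance per lesion relative to a true-change variance of 1, set at 0, 1 or 2.
- Sensitivity is related to the other lesions only through c.

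Let C = w + (1−w)c, V₀ = w² + (1−w)² + 2w(1−w)c, and V = V₀ + k[w² + (1−w)²]. The ratio of unmatched to matched correlation is

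F = √(1+k) × [(1−m) + mC] / √[(1−m)(1+k) + mV].

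Middle case (w = 0.6, c = 0.4, k = 1, m = 0.5): C = 0.76, V₀ = 0.712, V = 0.712 + 0.52 = 1.232. Then F = 1.414 × 0.88 / √1.616 = 0.979, and a matched correlation of 0.50 becomes 0.489.

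| Noise k | F over the 9 cells, m = 0.5 | Cells with F < 1 |
|---|---|---|
| 0 | 0.908–0.978 | 9 of 9 |
| 1 | 0.930–1.008 | 8 of 9 |
| 2 | 0.937–1.018 | 6 of 9 |

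Dependence on the mix, k = 1, at m = 0.25, 0.50 and 0.75: 0.494, 0.489, 0.486 in the middle case; 0.483, 0.465, 0.447 in the least favourable case (w = 0.5, c = 0.3).

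**Noise that falls with measured area.** A smaller region gives a noisier thickness. With noise k/w for the largest lesion alone and k for the full zone,

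F = [(1−m) + mC] × √{[(1−m)(1+k) + m(1+k/w)] / [(1−m)(1+k) + m(V₀+k)]}.

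Middle case, k = 1: 0.88 × √(2.333 / 1.856) = 0.987, so 0.50 becomes 0.493. Over the grid, F is 0.966–1.010 at k = 1 (below 1 in 7 of 9 cells) and 0.979–1.032 at k = 2 (5 of 9).

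**A less favourable case.** Take three equally weighted lesions, no noise, and c = 0.3, 0.5 or 0.7. If all eyes are multifocal, F = √[(1+2c)/3], and 0.50 becomes 0.37, 0.41 or 0.45. If half are, it becomes 0.44, 0.46 or 0.47.

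**Sampling error for scale.** By Fisher's z at n = 50: artanh(0.50) = 0.549, and 1.96/√47 = 0.286. The limits are tanh(0.263) = 0.26 and tanh(0.835) = 0.68.

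**The case for a change.** The strongest case for acting is that the qualifier is missing from the thickness items everywhere they appear, so it is not a one-off slip. A mismatch would be systematic, and naming the lesion would take one sentence. OCT is already scheduled at every visit, and section 5.2 says that test spots can be mapped to the fundus and to FAF images.

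Most of this stands as description. The wording is asymmetric, the region is unstated, and the plural in the sensitivity endpoint leaves open how many lesions it covers. It does not follow that the plan would give a worse answer:

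- Section 6.2.1 refers to an imaging manual, 7.3 to a TSAP and 7.4 to a cumulative analysis plan. None is in the public document, and region rules commonly sit in such papers. Sections 2.2.1, 2.2.2 and 7.3.3 appear only as headings in this copy, so their content cannot be counted as absent.
- The gain from forcing a match is not established. With area-dependent noise at k = 2, the matched correlation is the lower one in 4 of 9 cells.
- The work is not obviously trivial. If the reading centre does not already segment by lesion, matching means two layers, two zones, SS-OCT and SD-OCT, at baseline and three follow-up visits. The document does not cost this.

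**Conclusion.** No change is needed. This is an unstated region of interest that the reading centre and the trial statisticians would sensibly settle, most naturally by using the lesion(s) already chosen for microperimetry. No rule in the plan is shown to give a wrong result.

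If thickness were in fact pooled over lesions, the middle-case effect is about 0.01 on a correlation of 0.50. It is larger under harsher assumptions: down to 0.45 in the noise-free two-lesion grid with half the eyes multifocal, and to 0.37 if every eye had three equally weighted lesions and no noise. It is nil or slightly reversed under others. All these values lie inside the 0.26 to 0.68 interval that 50 patients give. The analyses are exploratory, the sample size is unaffected, and the descriptive thickness endpoints are not shown to be biased.

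The sizes rest wholly on assumed lesion weights, between-lesion correlations, noise and multifocal share. The conclusion leans less on them than on the text: it is silent about the lesion used for thickness and does not prescribe a mismatch.

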7.3.2 Secondary endpoint analyses

The secondary endpoints (see [Section 2.1.3](#)) will be analysed descriptively.

Correlations between the secondary endpoints and continuous baseline characteristics will be investigated if necessary.

7.3.3 Further endpoint analyses

7.3.4 Safety analyses

AEs will be coded using the Medical Dictionary for Drug Regulatory Activities (MedDRA). Standard BI summary tables and listings will be produced.

AEs recorded prior to Visit 2 will be assigned to the screening period, and AEs occurring after Visit 1 but prior to the study termination date will be assigned to the observation period. Note that AEs occurring after the last per protocol contact but entered before database lock will not be captured in the trial database.

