2.2 FURTHER OBJECTIVES AND FURTHER ENDPOINTS

2.2.1 Further objectives

2.2.2 Further endpoints

3. DESCRIPTION OF DESIGN AND TRIAL POPULATION

3.1 OVERALL STUDY DESIGN AND PLAN

This is a US / Europe, multi-center observational study with an enrollment target of 50 patients with GA secondary to AMD who are not receiving treatment for GA.

The observational period is dependent on the potential future availability of approved treatments for GA; in the absence of an approved therapy, this observational study may extend to 12 months. Visual function and anatomic measures will be collected at baseline, 3 months, 6 months, and 12 months. The study will consist of a screening period of up to 28 days (Days -28 to -1) and an observation period of maximally 12 months.

Enrolled patients must satisfy all eligibility criteria at both the screening period and the Day 1 visit. As part of the screening process, the Central Reading Center (CRC) will evaluate color fundus photographs, FAF images, to provide an objective assessment of patient eligibility. Patients must also meet BCVA and other eligibility criteria. Screen-failed patients can rescreen up to two additional times to qualify for study participation. One eye will be chosen as the study eye. If both eyes are eligible, the eye with the better visual function (as determined by the investigator and the patient) will be the study eye; if both eyes have the same visual function, the eye with the larger area of GA will be selected as the study eye (data will be collected on both eyes but analysed for the study eye only).

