5.1.3.2 Adverse event collection and reporting

AE Collection

The investigator shall maintain and keep detailed records of all AEs in the patient files. The following must be collected and documented on the appropriate CRF(s) by the investigator:

- From signing the informed consent onwards until the individual patient’s end of study:
-all AEs (serious and non-serious).
- After the individual patient’s end of study:
the investigator does not need to actively monitor the patient for AEs but should only report related SAEs of which the investigator may become aware of by any means of communication, e.g. phone call. Those AEs should however, not be reported in the CRF.

Information required

For each AE, the investigator should provide the information requested on the appropriate eCRF pages. The investigator should determine the causal relationship to the study procedures.

If such abnormalities already pre-exist prior to study inclusion they will be considered as baseline conditions and should be collected in the eCRF only.

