6.2 DETAILS OF STUDY PROCEDURES AT SELECTED VISITS

Patients must sign Informed Consent before any study related procedures are performed.

Signing of the Informed Consent is not necessarily the start of the screening visit.

Once Visit 1 procedures are complete inclusion/exclusion criteria must be reviewed. If patient meets inclusion/exclusion criteria, patient should be contacted to schedule next visit.

If patient does not meet inclusion/exclusion criteria the patient must be recorded in CRFs as a screen failure.

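### Section 7.3.4 ends screening at Visit 2 but starts observation after Visit 1, so adverse events between the two visits can fall in both periods

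*Combined protocol and SAP*

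**What the plan says.** Section 7.3.4 (Safety analyses) sets the period rule in one sentence: "AEs recorded prior to Visit 2 will be assigned to the screening period, and AEs occurring after Visit 1 but prior to the study" (the latter, up to the date of study termination, are placed in observation). The first half cuts at Visit 2 and refers to recording. The second half cuts at Visit 1 and refers to occurrence.

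The design is described differently elsewhere in the protocol:

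- The Flow Chart lists Visit 1 alone under Screening, at weeks -4 to -1. Visit 2, labelled Baseline, is the first visit under Observation Period.
- Section 3.1: "The study will consist of a screening period of up to 28 days (Days -28 to -1) and an observation period" that lasts at most 12 months. The same section adds: "Enrolled patients must satisfy all eligibility criteria at both the screening period and the Day 1 visit".
- Section 7.3.1, for the primary endpoints: "baseline is defined as the measurement obtained at Visit 2". Section 5.2 allows a Visit 1 value when the Visit 2 value is missing. That fallback concerns the measurement and does not move the start of observation.

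Under section 5.1.3.2, adverse events are collected over this span: "From signing the informed consent onwards until the individual patient" reaches the end of study. Section 6.2 notes: "Signing of the Informed Consent is not necessarily the start of the screening visit".

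**The concern.** Two consecutive periods need one boundary, and section 7.3.4 gives two. The time between Visit 1 and Visit 2 meets the observation rule, although the Flow Chart and section 3.1 place it in screening. Events from this time are collected, so the conflict affects data that will exist.

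Adverse events are the only safety criterion in the synopsis, and section 7.3.4 itself divides them by period. With no rule of precedence, two programmers could follow the sentence faithfully and produce different counts by period from the same database. The observation-period table could also include events that arose before baseline.

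**Working it through.** The plan gives no figure to reproduce. The check applies the two rules to each possible timing of an event and compares the result with the design.

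**Length of the interval.** The Flow Chart puts Visit 1 no earlier than week -4, and 4 × 7 = 28 days. This agrees with the maximum of 28 days in section 3.1. The week -1 label suggests about 7 days at the short end, but section 3.1 states no minimum, so only the upper limit is used here.

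**Reading A: recorded simply means occurring.**

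- Onset up to Visit 1: screening only.
- Onset between Visits 1 and 2: both periods.
- Onset from Visit 2: observation only.

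Every event with onset between the visits is assigned twice, and nothing is left out.

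**Reading B: recorded means the date of recording.**

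1. Onset up to Visit 1, recorded before Visit 2: screening only.
2. Onset between the visits, recorded before Visit 2: both periods.
3. Onset between the visits, recorded at Visit 2 or later: observation only.
4. Onset up to Visit 1, recorded at Visit 2 or later: neither period.
5. Onset from Visit 2: observation only.

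By the Flow Chart and section 3.1, cases 1 to 4 belong to screening and case 5 to observation. The written rule agrees with the design in cases 1 and 5 only. Case 4 can arise because collection starts at consent, which may precede the screening visit. The documents do not show how events divide between cases 2 and 3.

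**Common to both readings.** Every event with onset between the visits meets the observation rule. So does an event after Visit 1 in a patient who never reaches Visit 2, which matters only if such patients' events are tabulated. Events with onset from Visit 2 are not affected by the mismatch.

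**Search for a rule of precedence.** None is given. Section 7.3 mentions the trial statistical analysis plan (TSAP) only in connection with protocol violations. The amendment description in section 11.1 lists no change to section 7.3.4.

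**The case against.** The best defence is that this is a slip of one word. If the second half had named Visit 2, the sentence would fit the design, and the intended boundary can be recovered from the Flow Chart and section 3.1. The output consists of the sponsor's standard summary tables and listings, whose conventions are not shown and may already settle the matter. There is no treatment (section 4.1) and no confirmatory test (section 7.2), and no endpoint uses the adverse event periods.

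Most of this stands and limits the point to a minor one. It does not remove it. The rule as written contradicts the design, and neither the TSAP nor the table conventions are said to resolve the conflict. If the sponsor did intend observation to begin after Visit 1, the screening half would be the part in error, so one half must change in either case.

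A second objection is that reading the word recorded literally is strained. The next sentence of section 7.3.4 uses a different verb for data entry: "Note that AEs occurring after the last per protocol contact but entered before database lock will not be captured in the trial database". Reading A may therefore be what was meant. Under that reading cases 3 and 4 disappear, but the overlap remains and covers every event with onset between the visits.

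A reader might also infer that rescreening multiplies the overlap, since section 3.1 says: "Screen-failed patients can rescreen up to two additional times to qualify for study participation". The documents do not support this. An attempt that fails before Visit 2 has no interval from Visit 1 to Visit 2, so the 28 days cannot be multiplied by the number of attempts.

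**Conclusion.** The inconsistency is real and minor. It is a conflict of wording between section 7.3.4 and the design, over an interval of up to 28 days before Visit 2. The overlap holds whichever way the word recorded is read. The case of an event in neither period depends on the literal reading. Taking the Day 1 visit in section 3.1 to be Visit 2 is an inference from the Flow Chart, not an express statement.

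Only adverse event summaries by period are affected. Overall totals that count each event once, and all endpoints, are unaffected.

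Two stronger conclusions are tempting and should not be drawn. One is a count or percentage of misassigned events. The documents give no event rate, and a ratio of 28 days to follow-up would be a share of time, not of events; the 12 months is also only a maximum. The other is that the end of the observation period must be redefined because the study termination date is not defined. That is a separate matter from the mismatch at the start, and the obvious substitute, the patient's end of study in section 5.1.3.2, is not defined either.

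**What to change.** Use onset date for both periods and a single boundary at Visit 2, for example:

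*Adverse events with onset from informed consent to before Visit 2, including all adverse events of patients who do not reach Visit 2, are assigned to the screening period. Adverse events with onset at or after Visit 2 are assigned to the observation period.*

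The existing upper limit of the observation period stays as it is. With this wording, cases 1 to 4 go to screening and case 5 to observation, so each event within that limit falls in exactly one period.

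The change can be made in section 7.3.4 or in the TSAP. It costs one sentence. No new data or change at the sites is needed, because adverse events are already collected from consent onwards.
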